6.2.3.1 Additional analysis

Given that there is no significant site effect for DBC-18PENDL02, no significant difference for BD PN between DBC-18PENDL02 and DBC-18PENDL01, and no significant difference between any comparator PNs, data from DBC-18PENDL02 and DBC-18PENDL01 will be combined for analysis. An overall result combining all PNs in the two studies will be presented.

6.2.4 Analysis of Exploratory Objectives (Delivery time, Total injection time, Needle Breaking, and Non-Comparative Questionnaire)

6.2.4.1 Delivery time and Total injection time

A mixed effect model will be used (fixed effects of pen needle type, abdomen site, order of pair, order of pen needle within pair and random subject effect) to estimate average difference (BD Nano PN - each comparator PN) in delivery time and total injection time. The interaction of PN and clinical site will be verified. If the interaction is significant, comparison results will be presented by site. If the interaction is not significant, it will be dropped from the model and clinical site will be included as main effect. If the site difference is significant, mean delivery time and mean total injection time will be presented by site for each PN. Otherwise, the site effect will be dropped from the model. A Box-Cox transformation might be used to normalize the data if necessary. The upper bound of the confidence interval will be compared to 0: superiority will be concluded given that the upper bound of the 95% interval for the average difference is < 0 seconds.

Given that there is no significant site effect for DBC-18PENDL02, no significant difference for BD PN between DBC-18PENDL02 and DBC-18PENDL01, and no significant difference between any comparator PNs, data from DBC-18PENDL02 and DBC-18PENDL01 will be combined for analysis. An overall result combining all PNs in the two studies will be presented.

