## 3.4 Treatment Allocation and Methods to Reduce Bias

### 3.4.1 Randomization

The order of the pen needles within the pairs and abdominal injection sites for each pair will be randomized across each Subject. Injection site diagram, will be provided to assist in complying with site randomization.

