Analysis for time to deliver and dwell time: A mixed effect model will be used (fixed effects of pen needle type, abdomen site, order of pair, order of pen needle within pair and random Subject effect) to estimate average difference (BD PN – each Comparator PN) in time to deliver and dwell time. The upper bound of the confidence interval will be compared to 0: superiority will be concluded given that the upper bound of the 95% interval for the average difference is  $< 0$  seconds.

Other exploratory endpoints will be summarized.

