2.3 Study Design

This is a subject partially blinded, block randomized, prospective, single-visit, multi-center study to compare user experiences with BD NanoTM PRO pen needle vs. three (3) thinner commercially available comparator pen needles (Artsana Insupen[®] Extr3me 33G, Artsana Insupen[®] Extr3me 34G and the Simple Diagnostics Comfort EZ^{TM} 33G Pen Needles). The study will include up to 146 study subjects having Type 1 or Type 2 diabetes. Study conduct will consist of one 60 to 120 minute site visit in which pre-set doses of saline will be abdominally delivered by subjects via a reusable insulin pen device. All pen needles will be attached by study staff and pen needle outer cover and inner shield will be removed for subjects. Subjects are to perform 12 injections into the abdomen (6 pairs of injections). Pairs of injections will be evaluated and each pair will contain one BD NanoTM PRO and one comparator pen needle. Within the 12 injections, each comparator will be injected twice, therefore each subject will experience 2 of each of the following pairs:

- BD NanoTM PRO pen needle v
s Artsana Insupen[®] Extr3me 4mm × 33G × 2
- BD NanoTM PRO pen needle vs Artsana Insupen[®] Extr3me 3.5mm \times 34G \times 2
- BD NanoTM PRO pen needle vs Simple Diagnostics Comfort EZ^{TM} 4mm × 33G × 2

Subjects will not see pen needle labels or be informed which pen needle is being used to inject. The BD NanoTM PRO has a distinct configuration and subjects will most likely notice the difference vs the comparators. Subjects will not be informed of the BD's or the comparator's pen needle brand, length or gauge. The pen needle order within the pairs of injections will be randomized for each subject and the pairs will be randomized to various abdominal injection sites within each subject. Besides being informed of the requirement to insert the pen needles "straight-in" (perpendicular), subjects will be instructed to use their usual injection technique.

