6.2 Analysis Method

This section provides a detailed description of the statistical analysis that will be performed in this study.

Unless otherwise stated, all the statistical tests are two-sided at a significance level of 5%.

Summary statistics (number of observations, mean, 95% CI for mean, median, standard deviation and range) for all quantitative responses will be presented in tables. Frequency tables with number of observations, percentage of total will be created for all discrete responses. If a modeling approach is applied, the fitted mean with 95% CI will be presented in tables.

Bar plots may be provided for some responses.

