6.2.3 Analysis of Needle Bending and Leakage

If there is a sufficient number of occurrences for a modeling approach, analysis will be performed using a binary logistic regression with random subject effect and fixed pen needle type effect, pair order effect,

DBC-18PENDL02

PN order effect within pair and abdomen site effect. The interaction of PN and clinical site will be verified. If the interaction is significant, multiple comparisons for site difference by each PN will be conducted and results will be presented by site for PNs with significant site difference. If the interaction is not significant, it will be dropped from the model and clinical site will be included as main effect. If the site difference is significant, results will be presented by site for each PN. Otherwise, the site effect will be dropped from the model. The average difference in percentage of occurrence with BD PN and each comparator pen needle will be calculated with 95% confidence interval and assessed for statistical significance. The upper bound of the confidence interval will be compared to 0: superiority will be concluded given that the upper bound of the 95% confidence interval for the difference in proportions is < 0%.

If a modeling approach cannot be applied, a proportion test will be used to detect the difference in percentage of occurrence between sites for each PN. If there is no significant difference, the difference in percentage of occurrence with BD PN and each comparator pen needle will be calculated with 95% confidence interval (Score method) and assessed for statistical significance.

PNemmeanSEdfasymp.LCLasymp.UCLBD Nano0.0794299813925529Inf-2729353527293535Artsana 33G0.079425958632818Inf-1692001316920013Artsana 34G0.0794449111568566Inf-2267397322673973Simple Diagnostics0.0794080312153341Inf-2382011023820111

Results are given on the logit (not the response) scale. Confidence level used: 0.95

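### The injection-time models have no random pair-within-subject effect, so their BD-minus-comparator intervals would be conservative if injections within a pair share extra variation (minor)

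*SAP*

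**What the plan says.** SAP 6.2.4.1 models delivery time and total injection time with "fixed effects of pen needle type, abdomen site, order of pair, order of pen needle within pair and random subject effect". Protocol 13.3 gives the same structure for time to deliver and dwell time: "fixed effects of pen needle type, abdomen site, order of pair, order of pen needle within pair and random Subject effect". The leakage and bending model in SAP 6.2.3 is "a binary logistic regression with random subject effect and fixed pen needle type effect, pair order effect", with further fixed terms for needle order within pair and abdomen site. Subject is the only random term in each.

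The design is paired. SAP 2.3 states: "Subjects are to perform 12 injections into the abdomen (6 pairs of injections". Each pair holds one BD needle and one comparator, and each comparator appears in two pairs. Protocol 3.4.1 makes the pair the unit for order and site: "The order of the pen needles within the pairs and abdominal injection sites for each pair will be randomized across each Subject".

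Protocol 3.3 and SAP 2.5.3 set no formal acceptance criterion for the time endpoints. SAP 6.2.4.1 nevertheless states a decision rule: "superiority will be concluded given that the upper bound of the 95% interval for the average difference is < 0 seconds".

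**The concern.** The fixed terms for pair order, order within pair and abdomen site remove effects averaged over all subjects. They cannot remove what two injections share because they belong to the same pair in the same person, such as that person's tissue at the assigned site or their pace and technique at that point in the visit. Protocol 6.2.1 lets subjects use their usual technique and allows an angled insertion or a skin pinch, so some variation of this kind is plausible.

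A subject-only model treats the two injections of a pair as no more alike than any two injections by that subject. Every BD-versus-comparator contrast has a within-pair component, so positive pair variance would make the model overstate its standard error and weight the data less than optimally. The cost would be a real difference in injection time that is easier to miss.

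**Working it through.** **Inputs.** The design is 133 subjects (SAP 3), six pairs each, with six BD injections and two of each comparator per subject (SAP 2.3), and two-sided 95% intervals (SAP 6.2). The plan gives no SD, power or pair variance for injection time. Its 133 comes from the pain calculation, which reproduces: Φ(10/(50/√266) − 1.96) = Φ(1.30) = 0.90, and 266 pairs / 2 per subject = 133.

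**Assumption.** Let σp² be the pair variance within subject and σe² the residual variance. Scale them so that σp² + σe² = 1, and let ρ = σp² be the pair share of within-subject variance. The range 0 to 0.5 is assumed.

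**Per-subject variance of BD minus one comparator, before the other fixed effects**

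1. *True variance of the planned estimator.* The BD mean has variance 1/6 and the comparator mean 1/2. They share two pairs, so their covariance is 2 × (1/6) × (1/2) × ρ = ρ/6. The variance is 1/6 + 1/2 − 2ρ/6 = (2/3)(1 − ρ/2).
2. *Variance that the subject-only model reports.* The expected within-subject mean square on 12 injections is σe² + (10/11)σp² = 1 − ρ/11; the subject component absorbs the other σp²/11. The reported variance is (2/3)(1 − ρ/11).
3. *Variance with a random pair effect.* Within-pair differences estimate each BD-minus-comparator effect with variance 1 − ρ. Pair sums add information on contrasts among comparators, with variance 2σp² + σe² = 1 + ρ. Combined, the variance is (1 − ρ)/3 + (1 − ρ²)/3 = (1 − ρ)(2 + ρ)/3.

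**Example, ρ = 0.3.** Reported: (2/3)(1 − 0.3/11) = 0.6485. True: (2/3)(0.85) = 0.5667. With pair effect: 0.7 × 2.3/3 = 0.5367. The SE ratios are √(0.6485/0.5667) = 1.070, √(0.5667/0.5367) = 1.028 and √(0.6485/0.5367) = 1.099.

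**Full design.** Generalised least squares on 133 × 6 × 2 injections with all the SAP's fixed effects, assuming six abdominal sites, gives the table below. The closed forms agree to within 0.001, and subject variances of 0 and 1 give the same ratios.

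| ρ | Reported SE / true SE | Coverage of nominal 95% CI | True SE / SE with pair effect | Equivalent extra subjects | Reported CI width / width with pair effect |
|---|---|---|---|---|---|
| 0 | 1.000 | 95.0% | 1.000 | 0% | 1.000 |
| 0.1 | 1.021 | 95.5% | 1.003 | 0.5% | 1.024 |
| 0.2 | 1.045 | 95.9% | 1.011 | 2.3% | 1.056 |
| 0.3 | 1.070 | 96.4% | 1.028 | 5.6% | 1.100 |
| 0.4 | 1.098 | 96.9% | 1.054 | 11% | 1.157 |
| 0.5 | 1.129 | 97.3% | 1.096 | 20% | 1.237 |

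Coverage is 2Φ(1.96 × ratio) − 1; at ρ = 0.5 this is 2Φ(2.21) − 1 = 97.3%. Extra subjects is the squared efficiency ratio minus 1; at ρ = 0.5 this is 1.096² − 1 = 20%.

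**Leakage.** Leakage was simulated at the prior-study rates in SAP 3 (1.0% for BD; 6.4%, 8.4% and 22.1% for the comparators). Raising the pair variance from 0 to 2 on the logit scale (an assumed range) changes the true SE of the observed BD-comparator difference by 0.5% to 2.4%. Bending cannot be sized, because the documents give no bending rate.

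**The case against.** The strongest reply is that the omission may cost nothing. The model already adjusts for subject, pair order, order within pair and site. Only residual subject-by-pair variation is left, and nothing in the documents shows that it exists. The two injections are also not immediately consecutive: Protocol 6.2.1 places leakage collection and bend inspection after each injection and requires at least 1 inch from the previous one. Shares of 40% to 50% have no documentary support. All of this stands, and it is why the point is conditional.

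Several stronger readings are tempting, and the documents do not support them.

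- *The error bars are simply wrong.* That needs a positive pair variance, which is not given.
- *A false superiority claim could follow.* The error runs the other way: over the assumed range the two-sided error rate falls from 5% to between 4.5% and 2.7%.
- *The blocking is thrown away.* Every subject uses every needle and the subject effect is kept. The real loss of efficiency is 0.3% to 9.6% in SE.
- *The plan wastes the equivalent of 5% to 53% more subjects.* Squaring the last column of the table gives those figures, but they mix an overstated SE with real loss. The real loss is 0.5% to 20%.
- *The pooling conditions in SAP 6.2.4.1 are compromised.* Comparator-versus-comparator SEs are 0.4% to 2.1% too small, a test size of 5.1% to 5.5%. Pooling requires no significant difference, so this makes pooling slightly less likely.
- *The secondary endpoints are materially affected.* The leakage effect is small, and SAP 6.2.3 already provides a non-model fallback when occurrences are few.

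**Conclusion.** The point holds as a minor, conditional refinement. The delivery-time and total-time models omit a block that the randomisation uses. If the pair explains 10% to 50% of within-subject variance, the planned BD-minus-comparator interval is 2% to 24% wider than it need be: a reported SE 2% to 13% above its true value, combined with an efficiency loss of 0.3% to 9.6%. At zero pair variance the two models agree.

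The figures assume a linear model on whatever scale is analysed, complete data from 133 subjects, six sites, and injections within a pair at least as alike as injections from different pairs. Under that last assumption the omission is conservative for every BD-versus-comparator contrast.

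Injection time is exploratory. Primary pain and secondary force are rated once per pair, so the omission does not reach them.

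**What to change.** In SAP 6.2.4.1, and in the matching paragraph of Protocol 13.3, add a random effect of pair nested within subject, for example (1 | subject/pair). State that the model reverts to subject only if the pair variance is estimated as zero.

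For leakage and bending (SAP 6.2.3), keep the planned model and add the pair term only as a sensitivity analysis where it can be estimated.

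The cost is a sentence or two of wording and one variance component. No new data are needed, because pair order is already a model term and so identifies the pair within each subject. The small downside is that a pair variance may be hard to estimate for rare binary outcomes with two observations per pair, which is why it should not enter the main leakage and bending model.

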6.2.4.2 Needle Breaking

The number and proportion of needle breaking occurrence for each pen needle type will be summarized. In addition, a 95% confidence interval for difference in proportions between BD Nano PN and each comparator PN will be calculated using the score method for independent proportions. Site effect will be verified in a similar way with needle bending.

6.2.4.3 Non-Comparative Questionnaire

All the responses from Non-Comparative Questionnaire will be summarized with number and percentage of each option. Data from DBC-18PENDL02 and DBC-18PENDL01 will be combined for analysis if possible.

7 Safety Analysis

Data listings will be provided for any adverse events and serious adverse events in Appendix. The events will also be summarized descriptively per pen needle type. No safety analysis is planned.

8 Example Reports

This section provide examples of tables and graphical representations that will be provided in the study statistical report. These table examples were generated using the sample data available from the data base test framework which do not provide an exhaustive or representative example of the values and levels that will be obtained in the study. They are intended to provide illustrative examples of the tables and figures that will be included in the final statistical analysis report.

8.1 Study Execution

The number of subjects enrolled, randomized, withdrawn, who completed and who are excluded will be provided as in Table 2. More details on specific data may be provided in Summary Statistics and Appendix.

8.1.1 Analysis Population Set(s)

1 1 (1	.)
Subject.Population	Ν	Comments
Subjects Enrolled	252	none
Subjects who did not meet I/E Criteria	6	none
Subjects Randomized	245	none
Subjects Withdrawn	5	none
Subjects who Completed the Study	240	none
Subjects Excluded from Analysis	1	Give Reasons

Table 1: Population Disposition (Example only)

Table 2: Number of completed pairs of injection per Comparator PN (Example only)

Comparator	N.pairs
Artsana 33G	265
Artsana 34G	265
Simple Diagnostics	265

8.1.2 Data Exclusions

All exclusions will be listed with reason(s) for exclusion.

8.1.3 Executive Summary

A high level summary will be provided for each objective/endpoint (example below).

Primary Objective (examples only):

• *Injection Pain:* The lower bound of the CI for the average relative pain comparison between BD Nano[™] PRO and Artsana Insupen[®] 33G met both non-inferiority and superiority criteria.

Secondary Objectives (examples only):

- *Injection force:* The lower bound of the CI for the average difference in rating of BD Nano[™] PRO and Artsana Insupen[®] 33G injection force met the superiority criterion.
- *Needle Bending:* The upper bound of the CI for the average difference in percentage of needle bending occurrence with BD Nano[™] PRO and Artsana Insupen[®] 33G met the superiority criterion.
- Leakage: The upper bound of the CI for the average difference in percentage of leakage occurrence with BD Nano[™] PRO and Artsana Insupen[®] 33G met the superiority criterion.

In addition, a summary table for all primary and secondary objectives will be presented as in Table 3 (Example only). A blue check mark (\checkmark) indicates that the acceptance criterion is met, while a red X mark (\bigstar) indicates that the acceptance criterion is not met.

Objective	Comparison	
Primary Objective		
Injection Pain (Non-inferiority)	BD Nano vs Artsana 33G	 Image: A set of the set of the
Injection Pain (Non-inferiority)	BD Nano vs Artsana 34G	 Image: A set of the set of the
Injection Pain (Non-inferiority)	BD Nano vs Simple Diagnostics	 Image: A set of the set of the
Secondary Objective		
Injection Pain (Superiority)	BD Nano vs Artsana 33G	×
Injection Pain (Superiority)	BD Nano vs Artsana 34G	×
Injection Pain (Superiority)	BD Nano vs Simple Diagnostics	×
Injection force	BD Nano vs Artsana 33G	 Image: A set of the set of the
Injection force	BD Nano vs Artsana 34G	 Image: A set of the set of the
Injection force	BD Nano vs Simple Diagnostics	 Image: A set of the set of the
Needle Bending	BD Nano vs Artsana 33G	 Image: A set of the set of the
Needle Bending	BD Nano vs Artsana 34G	 Image: A set of the set of the
Needle Bending	BD Nano vs Simple Diagnostics	 Image: A set of the set of the
Leakage	BD Nano vs Artsana 33G	 Image: A set of the set of the
Leakage	BD Nano vs Artsana 34G	 Image: A set of the set of the
Leakage	BD Nano vs Simple Diagnostics	V

Table 3: Results Summar	v of	primary	and	secondary	v ob	jectives	Exam	ole	only)
labie of itestates summar	, 01	printer,	ouro	becomaan.	$j \cup \omega$	10001100	1 2 2 2 2 2 2 2 2 2 2 2 2 2 2 2 2 2 2 2	10	orr,	1

8.2 Analysis and Results

8.2.1 Injection Pain

Summary statistics for the VAS scale will be presented as in Table 4.

The results for average relative VAS Score for BD NanoTM PRO vs comparator pen needle will be evaluated as presented in Table 5.

Table 4: Summary Statistics for observed 150mm Relative VAS Scores (Example only)

						、 -	۰,
Comparison	Ν	Mean	Std. Dev.	Mean 95% CI	Median	Median 95% CI	Range
BD Nano vs Artsana 33G	13	12.12	44.00	(-74.13, 98.36)	15.00	(-71.25, 101.25)	-75, 67.5
BD Nano vs Artsana $34G$	12	0.00	27.14	(-53.19, 53.19)	-7.50	(-60.69, 45.69)	-37.5, 45
BD Nano vs Simple Diagnostics	9	-10.00	41.59	(-91.52, 71.52)	-22.50	(-104.02, 59.02)	-52.5, 60

Table 5: Fitted Average Relative VAS score for BD Nano vs comparator pen needles (Example only)

Comparison	Fitted Mean	CI	Non-Inferiority	Superiority Conclusion
			Conclusion (Lower	(Lower bound $CI > 0$)
			bound $CI > -10$)	
BD Nano vs Artsana 33G	28.3	(17.1, 39.4)	TRUE	TRUE
BD Nano vs Artsana $34G$	19.2	(4.1, 34.4)	TRUE	TRUE
BD Nano vs Simple Diagnostics	26.1	(10.3, 42)	TRUE	TRUE

Preference VAS Scores with 95% confidence interval for the Average

Figure 2: Distribution of relative VAS scores with average and confidence interval per pen needle group and overall. Positive scores indicate that BD Next was preferred and negative scores indicate that the Current/Assigned PN was preferred. Note: This example graph comes from a study with different PN. Results for this study will reflect BD Nano performance.

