6.2.1 Analysis of Injection pain

For each comparator PN, a two-sided 95% confidence intervals will be calculated for the average rating. A modeling approach including data from all pairs of injections (all comparator PN included) will be used to analyze the data and estimate average ratings for each comparator PN adjusting for the pair order effect, BD order effect within pair (due to the often-observed bias towards favoring the last pen needle used in a pair), abdomen site effect, comparator PN effect and random subject effect. The interaction of PN and clinical site will be verified. If the interaction is significant, multiple comparisons for site difference by each PN will be conducted and results will be presented by site for PNs with significant site difference. If the interaction is not significant, it will be dropped from the model and clinical site will be included as main effect. If the site difference is significant, results will be presented by site for each PN. Otherwise, the site effect will be dropped from the model. Results will be tested for non-inferiority, followed by superiority:

- If the lower bound of the CI is > -10mm, we can conclude in non-inferiority.
- If the lower bound of the CI is > 0mm, we can conclude in superiority.

```
> ## Example for estimated pen needle subgroup means (Site effect not significant)
> ## if the lower CL is > -10, non-inferiority is satisfied
> ## if the lower CL is > 0, superiority is satisfied
> library(emmeans)
> emmeans(model.fit, ~Comparator)
```

Comparator	emmean	SE	df	lower.CL	upper.CL
Artsana 33G	26.87836	5.747502	140.26	15.515420	38.24129
Artsana 34G	20.09732	7.841233	139.57	4.594362	35.60027
Simple Diagnostics	22.40372	6.075449	140.25	10.392416	34.41502

Degrees-of-freedom method: kenward-roger Confidence level used: 0.95

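### SAP Table 4, the template for the observed pain scores, labels the mean or median ± 1.96 × SD as a 95% CI: a minor reporting error that leaves the non-inferiority decision untouched

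*SAP*

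**What the plan says.** SAP 6.2 sets the descriptive content for every quantitative response: "mean, 95% CI for mean, median, standard deviation and range". It promises no interval for the median.

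SAP 8.2.1 then fixes the presentation for the primary endpoint: "Summary statistics for the VAS scale will be presented as in Table 4". Table 4 has one row per comparator, giving N, mean, SD, an interval headed as the 95% CI of the mean, the median, an interval headed as the 95% CI of the median, and the range. The table is marked as an example. SAP Section 8 explains where such examples come from: "These table examples were generated using the sample data available from the data base test framework".

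The decision is read elsewhere. SAP 6.2.1 says: "A modeling approach including data from all pairs of injections (all comparator PN included) will be used to analyze the data". SAP 8.2.1 says that the average relative VAS score for the BD needle "vs comparator pen needle will be evaluated as presented in Table 5", and it is Table 5 that carries the non-inferiority and superiority columns.

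**The concern.** A 95% CI for a mean shrinks with √N. The Table 4 intervals do not: they have the width of a band expected to hold about 95% of single ratings if the ratings were normal. That is a different quantity from the one SAP 6.2 promises and from the one in the column headings.

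The table concerns the observed data for the primary endpoint, which is judged against a margin of −10 mm. If the same calculation were run on the study data, the report would show an interval of roughly ±98 mm in Table 4 beside a far narrower model-based interval in Table 5, both described as intervals for an average. A reader could not reconcile the two, and might wrongly take the raw data to contradict the model.

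**Working it through.** **Inputs.** N, means, SDs, medians, ranges and printed intervals come from SAP Table 4. The 266 pairs per comparator, 133 subjects and SD of about 50 mm come from SAP Section 3. The −75 to +75 mm scale comes from SAP 6.1.1. SAP 6.2 sets a two-sided 5% level, hence z = 1.96. The correlation ρ between a subject's two ratings of the same comparator is not given, so it is an assumption, taken over 0 to 1.

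**Step 1: reproduce the printed intervals as estimate ± 1.96 × SD.**

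| Row | N | SD | 1.96 × SD | Mean: computed | Mean: printed | Median: computed | Median: printed |
|---|---|---|---|---|---|---|---|
| Artsana 33G | 13 | 44.00 | 86.24 | 12.12 ± 86.24 = −74.12 to 98.36 | −74.13, 98.36 | 15.00 ± 86.24 = −71.24 to 101.24 | −71.25, 101.25 |
| Artsana 34G | 12 | 27.14 | 53.19 | 0.00 ± 53.19 = −53.19 to 53.19 | −53.19, 53.19 | −7.50 ± 53.19 = −60.69 to 45.69 | −60.69, 45.69 |
| Simple Diagnostics | 9 | 41.59 | 81.52 | −10.00 ± 81.52 = −91.52 to 71.52 | −91.52, 71.52 | −22.50 ± 81.52 = −104.02 to 59.02 | −104.02, 59.02 |

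Agreement is within 0.01 mm, which rounding of the printed means and SDs explains. The printed half-width divided by the SD is 1.960 in every case. The two intervals in a row share one SD, so these are three independent checks, not six. Using t(N−1) × SD instead would give half-widths of 95.87, 59.73 and 95.91, which do not match.

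**Step 2: check against the table's own range and scale.** The observed ranges are −75 to 67.5, −37.5 to 45 and −52.5 to 60. Of the 12 printed bounds, nine lie outside the range of their own row: five of six for the mean and four of six for the median. Four (98.36, −91.52, 101.25, −104.02) lie off the ±75 mm scale, where no mean or median can fall.

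**Step 3: the CI for the mean in the example rows, t × SD/√N, treating pairs as independent.**

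- Artsana 33G: 2.179 × 44.00/√13 = 26.6, giving −14.5 to 38.7. The printed interval is 86.2/26.6 = 3.2 times too wide.
- Artsana 34G: 2.201 × 27.14/√12 = 17.2, giving −17.2 to 17.2. The factor is 53.2/17.2 = 3.1.
- Simple Diagnostics: 2.306 × 41.59/√9 = 32.0, giving −42.0 to 22.0. The factor is 81.5/32.0 = 2.5.

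**Step 4: the mean at the planned size.** The Table 4 formula gives 1.96 × 50 = 98 mm whatever the sample size. With two ratings per subject, SE = 50 × √((1 + ρ)/266).

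| ρ (assumed) | SE (mm) | 1.96 × SE (mm) | 98 ÷ half-width |
|---|---|---|---|
| 0 | 3.066 | 6.01 | 16.3 |
| 0.5 | 3.755 | 7.36 | 13.3 |
| 1 | 4.336 | 8.50 | 11.5 |

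Using t quantiles for the correct interval changes the range only to 11.4 to 16.2.

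**Step 5: the median at the planned size.** Adding and subtracting 1.96 × SD gives no valid CI for a median at any N. As a yardstick only, under normality the SE of a median is about 1.253 × SD/√n. The half-widths are then 1.253 × 6.01 = 7.53 mm (n = 266) and 1.253 × 8.50 = 10.65 mm (effective n = 133), so the excess is 98/7.53 = 13.0 and 98/10.65 = 9.2.

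**Step 6: does the fault spread?** Other SAP output follows the standard error.

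- Table 15, age: 55.8 ± 1.96 × 13.0/√183 = 53.9 to 57.7, as printed.
- Table 17, diagnosed year: 14.2 ± 1.96 × 9.4/√182 = 12.8 to 15.6, as printed.
- Model example in SAP 6.2.1: 26.878 ± t(140.26) × 5.7475 = 15.52 to 38.24, as printed.
- Table 7, force: 1.4 ± 1.96 × 0.1 = 1.20 to 1.60, against a printed −0.1 to 2. It does not follow the Table 4 formula.

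**The case against.** The strongest reply is that the governing text is already right. SAP 6.2 asks for a CI for the mean, and nothing in the methods section prescribes ± 1.96 × SD. On this view Table 4 is a mock-up and the instruction to present results in its form fixes a layout, not a formula. Section 8 also contains plain placeholders. Table 7 pairs an SD of 0.1 with a range of −2 to 2, and Table 6 prints 132 of 330 as 43.9% when it is 40.0%. An interval of ±98 mm on a ±75 mm scale would probably be noticed when the report is checked.

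Much of this stands. It means that the example values carry no weight and that reuse of the formula is an inference. It does not remove the fault. Three rows agree with one wrong formula to 0.01 mm, which is how computed output behaves and not how typed placeholders do, and Section 8 says that the examples were generated from test data.

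A reader might infer more than the documents support:

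- **That the primary conclusion is at risk.** If the Table 4 interval were used for the decision at SD 50 mm, the mean would have to exceed 98 − 10 = 88 mm on a scale ending at 75 mm, so non-inferiority could never be shown. But SAP 6.2.1 and Table 5 read the decision from the fitted means, and Table 4 has no decision column. Protocol 13.3 leaves the modelling optional, but the SAP makes it definite.
- **That the SAP's intervals are wrong throughout.** Step 6 of the check shows otherwise.
- **That one factor covers both columns.** The 11.5 to 16.3 range holds for the mean only.

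**Conclusion.** The point holds as a minor reporting error, confined to Table 4. The two interval columns do not contain what their headings say, and the mean column departs from SAP 6.2. That the six printed intervals equal the estimate ± 1.96 × SD is certain to within rounding.

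The projected size at the planned sample rests on three assumptions: that the code behind the example is reused unchanged (it cannot be seen), that the SD is the planning value, and that ρ lies between 0 and 1. The sample size, error rate, non-inferiority rule and superiority rule are all unaffected. That the Table 5 intervals use t × SE is a reasonable inference from the SAP 6.2.1 example. Table 5 itself prints no standard error or degrees of freedom.

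**What to change.** Compute the mean interval in Table 4 as mean ± t × SE. Replace the median interval with a valid one, such as an order-statistic or bootstrap interval, or drop that column. Then regenerate Table 4 from the test data and confirm that no interval for the mean runs off the ±75 mm scale without reason.

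A subject-clustered standard error would respect the two ratings per subject, but it is optional in a descriptive table because the SAP 6.2.1 model already carries a random subject effect.

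The cost is a small code correction and one regenerated example table, with no change to design, sample size or decision rules.
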